Secondary Objectives	
To evaluate adverse events (AEs) suspected to be related to the crushed deferasirox FCT during the study
 
 • To assess the overall safety of crushed FCT of deferasirox • To assess the efficacy of deferasirox FCT treatment • To evaluate patient treatment satisfaction, palatability and gastrointestinal (GI) symptoms with Observer Reported Outcomes (ObsROs)
Study design	
 • The study employs an interventional, prospective, single arm, open label, global, multi-center, non-randomized trial design to monitor and assess the safety profile of the crushed deferasirox FCT in pediatric patients between age ≥2 to <6 with transfusional hemosiderosis over 24 weeks. This study will aim to enroll at least 40 patients. • The study will include a screening period (from Day 0-14) with two visits at least 7 days apart to assess eligibility of patients that are chelation naïve or on a prior iron chelator treatment other than DFX. For Patients on DFX treatment prior to study entry only one screening visit (screening visit 1) will occur to determine eligibility. Any current chelation therapy except deferasirox will be discontinued to undergo a 5-day washout period prior to commencing a 24 week treatment period with crushed deferasirox FCT. • All patients will have weekly visits for the first month to monitor renal function. Hepatic function will be assessed biweekly during the first month. Thereafter, monthly safety assessments will be performed, including the monitoring of serum ferritin values and trends in order to adapt patient treatment. • Eligibility, application of dosing standards and adjustments, as well as safety and serum ferritin assessments as specified in the protocol, will occur in accordance with the EU label throughout the study. • Patients will continue therapy up to 24 weeks.
Population	Pediatric patients between the age ≥2 to <6 years with transfusional hemosiderosis that are candidates for treatment with deferasirox.
Inclusion criteria	
Patients that are candidates for treatment with deferasirox
 
 • Patients ≥2 to <6 years old diagnosed with transfusional hemosiderosis • Documented history of red blood cell transfusions • Written informed consent/assent before any study-specific procedures. The

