4.1 Description of study design

The study employs an interventional, prospective, single arm, open label, global multi-center, non-randomized trial design to monitor and assess the safety profile of the crushed deferasirox FCT in pediatric patients between age ≥ 2 to < 6 years with transfusional hemosiderosis over 24 weeks.

This study will enroll at least 40 patients worldwide.

The study will include a screening period (from Day 0-14) with two visits at least 7 days apart to assess eligibility of patients that are chelation naïve or on a prior iron chelator treatment other than DFX. For Patients on DFX treatment prior to study entry only one screening visit (screening visit 1) will occur to determine eligibility and monitoring will be monthly after baseline assessments (day1). (For additional details refer to Section 8.1). Any current chelation therapy except deferasirox will be discontinued to undergo a 5-day washout period prior to commencing a 24 weeks treatment period with crushed deferasirox FCT, refer to Section 8.2 for additional details.

All patients will have weekly visits for the first month.

Safety assessments will be performed weekly after treatment initiation and thereafter monthly during the study. Monthly serum ferritin values and trends will be used to adapt the treatment of the patients together with safety data.

Patients will continue therapy for up to 24 weeks.

30-day follow-up

[figure not shown]
All patients must be followed for AEs and SAEs for 30 days after the last dose of study treatment to determine any potential treatment emergent adverse event regardless of whether the patient continues prescribed iron chelation treatment after last dose of study medication. Patients who discontinue study drug before week 24 should be scheduled for a visit within 7 days of ending treatment at which time all of the assessments listed for the final visit will be performed (end of treatment visit). At a minimum, all patients who discontinue study treatment, including those who refuse to return for a final visit, will be contacted for safety evaluations during the 30 days following the last dose of study drug.

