6.3.1.2 Elevations in serum creatinine

Serum creatinine must be monitored during the study as stated in visit schedule, refer to [Table 7-1](#).

For pediatric patients the following dose adjustment guidance applies:

- At single increase in serum creatinine (SCr) $>\text{ULN}$ and increased by $\geq 33\%$ from baseline, maintain DFX dose level and repeat the assessment at next visit as clinically indicated.
- If serum creatinine (SCr) $>\text{ULN}$ and increased by $\geq 33\%$ from baseline on 2 consecutive visits, deferasirox dose reduction by 7 mg/kg/day for the FCT is required.
- If after dose reduction, resolution of serum creatinine occurs ($<33\%$) and within normal limits, dose can be re-escalated to 100% of the last dose.

If increase in serum creatinine recurs again within 2 months according to guidelines above, therapy needs to be reduced to 50% of the last dose.

After 2 months, if the serum creatinine increase does not recur, study medication may be re-escalated to 100% of the last dose depending on the clinical judgement of the investigator.

If after an initial dose reduction, a progressive increase in serum creatinine beyond the ULN is observed, or SCr increase recurs, repeat at adequate dose, a treatment interruption is recommended.

After a treatment interruption, if serum creatinine falls below the age-appropriate ULN on two consecutive visits, it is recommended to resume therapy at 50% of the last dose, and after 1 month, if the serum creatinine increase does not recur, study medication can be returned to

100% of the last dose (including body weight adjustment if required) depending on the clinical judgement of the investigator.

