7.1 Study flow and visit schedule

Table 7-1 lists all of the assessments and indicates with an “X”, the visits when they are performed. All data obtained from these assessments must be supported in the patient’s source documentation. All data obtained from these assessments and noted with an “S” in the category column must be supported in the patient’s source documentation. The “D” in the category column must be supported in Novartis eCRF database.

No CRF will be used as a source document.

[figure not shown]

Table 7-1 Visit evaluation schedule

	Category	Protocol Section	Screening Visit 1 Day -14 to -8	Screening Visit 2 Day -7 to -1 (Newly Initiated DFX patients)	Baseline								End of study treatment (EoT)	30 day safety follow-up	
Visit Name			SV1	SV2*	Week 1 Day 1	Week 2 ± 3 days	Week 3 ± 3 days	Week 4 ± 3 days	Week 8 ± 7 days	Week 12 ± 7 days	Week 16 ± 7 days	Week 20 ± 7 days			
Obtain Informed Consent	D	11.3	X												
IRT(IWRS)	S	7.1.2.1	X	X	X	X	X	X	X	X	X	X			
Patient History															
Demography	D	7.1.2.3	X												
Inclusion/exclusion criteria	D	5.2, 5.3	X	X											
Medical History	D	7.1.2.3	X												
Transfusion Therapy ¹	D	6.4	X	Continuous – up to 30 days after last dose											
Prior and Concomitant Medications/Prior Chelation	D	6.4	X	Continuous – up to 30 days after last dose											
Surgical and Medical Procedures	D	6.4	X	Continuous – up to 30 days after last dose											
Physical Examination															
Physical Examination	S	7.2.2.1	X	X	X	X	X	X	X	X	X	X	X		
Height	D	7.2.2.3	X												X
Weight	D	7.2.2.3	X	X	X			X	X	X	X	X			X
Vital signs	D	7.2.2.2	X	X	X	X	X	X	X	X	X	X			X

Visit Name	Category	Protocol Section	Screening Visit 1	Screening Visit 2 Day -7 to -1 (Newly Initiated DFX patients)	Week 1 Day 1								End of study treatment (EoT) Week 24 ± 7 days	30 day safety follow-up	
			Day -14 to -8			Baseline	Week 2 ± 3 days	Week 3 ± 3 days	Week 4 ± 3 days	Week 8 ± 7 days	Week 12 ± 7 days	Week 16 ± 7 days	Week 20 ± 7 days		
mSICT	D	7.2.8	X ³				X		X					X	
Palatability questionnaire	D	7.2.8	X ³				X		X		X			X	
GI symptom questionnaire	D	7.2.8	X ³			X	X	X	X	X	X	X	X	X	
Study drug dispensation	D	6.3.1				X			X	X	X	X	X		
End of phase disposition	D			X	X									X	
Safety follow-up	D	4.1													X

* SV2 is applicable only to patients who are chelation naïve or are currently treated with chelation therapy other than deferasirox. Patients on prior deferasirox will NOT be subject to SV2

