7.1.4 Treatment period

Having completed the screening period, patients will be enrolled and eligibility registered in IRT. The patient will then begin therapy with crushed deferasirox FCT as per study protocol.

The treatment duration is 24 weeks. Study treatment is defined as crushed deferasirox FCT applied according to study protocol. Study-mandated evaluations and safety assessments will be performed every week for the first month and monthly thereafter in alignment with the visit schedule, see [Table 7-1](#).

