7.2.2.5.2 Clinical chemistry

Clinical chemistry samples will be collected at screening visit 1 and screening visit 2 and at visits as detailed in [Table 7-1](#).

The parameters to be measured at screening visits and at specific timepoints in the study are as follows:

Screening Visit 1 -All patients:

Parameters to be measured include serum creatinine, creatinine clearance, blood urea nitrogen or urea, total bilirubin, direct bilirubin, ALT, AST, alkaline phosphatase, uric acid, total protein, bicarbonate, albumin, chloride, glucose, inorganic phosphate, potassium, sodium, calcium, magnesium and serum ferritin.

Screening Visit 2_- (Only patients who are chelation naïve or treated with iron chelation other than deferasirox):

Parameters to be measured include serum creatinine, creatinine clearance and serum ferritin.

Study Visit Baseline (Week 1) – All patients:

Parameters to be measured include serum creatinine, creatinine clearance, blood urea nitrogen or urea, total bilirubin, direct bilirubin, ALT, AST, alkaline phosphatase uric acid, total protein, bicarbonate, albumin, chloride, glucose, inorganic phosphate, potassium, sodium, calcium, magnesium and serum ferritin.

Study Visit Week 2 – All patients:

Parameters to be measured include serum creatinine and creatinine clearance

Study Visit Week 3 – All patients:

Parameters to be measured include serum creatinine, creatinine clearance, total bilirubin, direct bilirubin, ALT, AST, uric acid, total protein, bicarbonate, albumin, chloride, glucose, inorganic phosphate, potassium, sodium, calcium, magnesium and alkaline phosphatase.

Study Visit Weeks 4, 8, 12, 16, 20 and end of treatment – All patients:

Parameters to be measured include serum creatinine, creatinine clearance, blood urea nitrogen or urea, total bilirubin, direct bilirubin, ALT, AST, alkaline phosphatase, uric acid, total protein, bicarbonate, albumin, chloride, glucose, inorganic phosphate, potassium, sodium, calcium, magnesium and serum ferritin.

Renal parameters are monitored weekly to establish a reliable pretreatment baseline and hepatic parameters are monitored biweekly for safety at the initiation of treatment.

For calculated CrCl from local labs where the enzymatic method is used to determine creatinine clearance the modified Schwartz formula will be used for analysis. This estimate will be provided each time serum creatinine is collected.

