1.1 Study design

This is an interventional, prospective, single arm, open label, global multi-center, non-randomized study to monitor and assess the safety profile of the crushed deferasirox FCT in pediatric patient's age between ≥ 2 to < 6 years with transfusional hemosiderosis over 24 weeks. The purpose of this study is to address a European Health Authorities (CHMP/PRAC) post-marketing requirement. CHMP/PRAC have requested Novartis for an additional post-authorization safety study to characterize the pediatric safety profile and to provide safety data on selected AEs (esophagitis, stomatitis, mouth ulceration, gastric ulcers, hemorrhage, abdominal pain, diarrhea, nausea, and vomiting).

This study will enroll at least 40 patients worldwide.

The study will include a screening period (from Day 0-14) with two visits at least 7 days apart to assess eligibility of patients that are chelation naïve or on a prior iron chelator treatment other than deferasirox (DFX). Only one screening visit (screening visit 1) will occur for prior DFX treated patients to determine eligibility. Any patients treated with prior chelation therapy except deferasirox will be discontinued to undergo a 5-day washout period before initiation of 24-week treatment period with crushed deferasirox FCT.

Safety assessments will be performed weekly after treatment initiation for the first 4 weeks and thereafter monthly during the study. Monthly serum ferritin values and trends will be used to adapt the treatment of the patients together with safety data. Patients will continue therapy for up to 24 weeks.

There is no interim analysis planned for this study.

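### One clause in Protocol Section 4.1 puts prior-deferasirox children on monthly monitoring from Day 1, against the weekly first-month schedule given everywhere else; it should be deleted

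*Protocol*

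**What the plan says.** Section 4.1 of the protocol explains that children on deferasirox before entry have only one screening visit. The same sentence then adds that for them "monitoring will be monthly after baseline assessments (day1", and points to Section 8.1 for detail. The following sentence, on the 5-day washout, points to Section 8.2.

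The next paragraph of Section 4.1 reads "All patients will have weekly visits for the first month". Elsewhere:

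- Protocol summary, study design: "All patients will have weekly visits for the first month to monitor renal function".
- Protocol Section 7.1.4: "Study-mandated evaluations and safety assessments will be performed every week for the first month and monthly thereafter".
- Protocol Section 7.2.2.5.2: the Week 2 chemistry list is headed "Study Visit Week 2 – All patients", and the Week 3 list is headed in the same way.
- Protocol Table 7-1, footnote: "Patients on prior deferasirox will NOT be subject to SV2". This is the only exemption for prior-deferasirox children visible in the table or its footnotes.
- SAP Section 1.1: "Safety assessments will be performed weekly after treatment initiation for the first 4 weeks and thereafter monthly during the study".

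**The concern.** The two statements in Section 4.1 cannot both hold for a child who enters on deferasirox. One gives monthly monitoring from Day 1 and the other gives weekly visits in the first month.

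The stake is mainly early safety monitoring in children aged 2 to under 6 years. Weeks 2 and 3 carry the early renal checks, and Week 3 carries the first post-baseline liver panel. Renal dose rules depend on those visits. Under Section 6.3.1.2, if creatinine is above the upper limit of normal and up by at least 33% "from baseline on 2 consecutive visits, deferasirox dose reduction by 7 mg/kg/day for the FCT is required". Section 6.3.1.3 has the same two-visit structure for creatinine clearance below 90 mL/min. Removing two early visits delays the point at which either rule can act.

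A lesser stake is data collection. Adverse events are sought by questioning at each visit (Section 8.1.1), and the GI symptom questionnaire is given at Weeks 2 and 3 (Section 7.2.8).

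**Working it through.** **Which schedule is intended?** The plan gives no figure on this point, so the statements are compared directly.

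| Place | First-month schedule | Limited by prior chelator? |
|---|---|---|
| Protocol 4.1, disputed clause | Monthly | Yes, prior deferasirox |
| Protocol 4.1, next paragraph | Weekly | No, all patients |
| Protocol summary, study design | Weekly | No, all patients |
| Protocol summary, therapy row | Weekly renal, biweekly hepatic | No restriction stated |
| Protocol 6.1 | Weekly, then monthly | No restriction stated |
| Protocol 7.1.4 | Weekly, then monthly | No restriction stated |
| Protocol 7.2.2.5.2 | Week 2 and Week 3 chemistry | No, all patients |
| SAP 1.1 | Weekly for 4 weeks, then monthly | No restriction stated |

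Three further points support the weekly reading.

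- Section 7.2.2.5.2 does restrict Screening Visit 2 by prior chelator. The authors marked a subgroup limit where they meant one.
- The protocol summary, Protocol Section 7.1.2 and SAP Section 1.1 repeat the single-screening-visit rule without the monthly clause.
- SAP Section 2.13.3 plans GI symptom score changes at Weeks 2 and 3 specifically for children pre-treated with deferasirox. That analysis needs the visits the clause would remove.

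**What would be lost if a site followed the clause?** Take monthly to mean Weeks 4, 8, 12, 16, 20 and 24.

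- Post-baseline treatment visits: Weeks 2, 3, 4, 8, 12, 16, 20 and 24 make 8; the monthly reading leaves 6. The loss is Weeks 2 and 3, which are 2 of the 3 first-month visits after baseline.
- Creatinine and creatinine clearance: 2 checks lost (Weeks 2 and 3). Liver panel: 1 lost (Week 3).
- GI symptom questionnaire: 2 of 8 post-baseline administrations lost.
- Scheduled adverse-event contacts: 8 visits plus the 30-day follow-up make 9, of which 2 are lost.
- Serum ferritin is not on the Week 2 or Week 3 lists, so the efficacy series loses nothing.

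**How long is the delay?** SAP Section 2.10.2 sets the target day for Week X as (X − 1) × 7 + 1.

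- Week 2: (2 − 1) × 7 + 1 = Day 8
- Week 3: (3 − 1) × 7 + 1 = Day 15
- Week 4: (4 − 1) × 7 + 1 = Day 22
- Week 8: (8 − 1) × 7 + 1 = Day 50

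Two-consecutive-visit rule (Sections 6.3.1.2 and 6.3.1.3), counting post-baseline visits only, by when the abnormality is first present:

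| First present | Weekly schedule acts | Monthly schedule acts | Delay |
|---|---|---|---|
| By Week 2 | Weeks 2 + 3, Day 15 | Weeks 4 + 8, Day 50 | 50 − 15 = 35 days |
| Between Weeks 2 and 3 | Weeks 3 + 4, Day 22 | Weeks 4 + 8, Day 50 | 50 − 22 = 28 days |
| Between Weeks 3 and 4 | Weeks 4 + 8, Day 50 | Weeks 4 + 8, Day 50 | 0 days |

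Table 7-1 allows ±3 days at Week 3 and ±7 days at Week 8. For the first row the delay then runs from 43 − 18 = 25 days to 57 − 12 = 45 days.

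For creatinine, Table 6-4 conflicts with Section 6.3.1.2: it requires the reduction after a single value at least 33% above baseline and above the upper limit of normal. Under that row the earliest action moves from Day 8 to Day 22, a delay of 14 days. With ±3-day windows at Weeks 2 and 4 it is 19 − 11 = 8 to 25 − 5 = 20 days.

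The first scheduled post-baseline liver test moves from Day 15 to Day 22, a delay of 7 days.

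**Cross-references.** Section 8.1 covers adverse events and Section 8.2 serious adverse events. The visit schedule is in Section 7.1 and the washout in Section 7.1.3. Both pointers in the paragraph are wrong.

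**The case against.** The contradiction cannot reasonably be denied; the argument on the other side concerns how much it matters.

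- **The documents already settle it.** The correction stands in the very next paragraph, Table 7-1 has Week 2 and Week 3 columns, and the laboratory lists name all patients. A site would have to put one clause in a sentence about screening ahead of all of these. This stands: sites are unlikely to have been misled.
- **The 35 days is a worst case.** It needs an abnormality already present by Week 2. A later onset gives 28 days or none. Section 7.1.9 allows unscheduled safety assessments at any time, so a child with an abnormal Week 4 value need not wait for Week 8. For creatinine, the single-value row of Table 6-4 cuts the worst case to 14 days. All of this stands, and the figure should be read only as an upper case at nominal visit days.
- **There is no demonstrated trial-level effect.** The documents give no expected share of prior-deferasirox children. The primary endpoint comes from the adverse-event page, so an early GI event can still be recorded at Week 4. This stands.
- **Some support is weaker than it looks.** The SAP 1.1 sentence is unrestricted but does not say all patients. The laboratory rows of Table 7-1 are missing from the text available for review, so the Week 2 and Week 3 laboratory content rests on Section 7.2.2.5.2. That the clause is leftover text is an inference, and other cross-references in the protocol are also wrong. These points stand, but none of them makes the clause correct.

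Section 2.6 recommends weekly creatinine checks in the first month for children at renal risk. It does not confine weekly checks to them, so it does not rescue the clause.

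**Conclusion.** The concern holds, as a minor one, with high confidence. The clause is operative text in the design section, is contradicted within that section, and conflicts with every other statement of the schedule found in the protocol and SAP. The intended first-month schedule is weekly for everyone.

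The consequences are conditional on a site following the clause: Weeks 2 and 3 lost for each affected child, and a delay to the earliest two-visit renal trigger of up to 35 days at nominal visit days. These figures assume that monthly means Weeks 4, 8, 12, 16, 20 and 24, that only post-baseline visits count towards the trigger, and that no unscheduled visit is made. The effect on the primary GI rate is not quantified and is probably small. The sample-size table (Table 10-1) is unaffected.

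**What to change.** In Section 4.1, end the sentence on prior-deferasirox children after the single screening visit and delete the words that say "monitoring will be monthly after baseline assessments (day1", together with the closing bracket. Table 7-1 then governs all patients, with Screening Visit 2 as the only visit prior-deferasirox children omit. In the same paragraph, change the pointer to Section 8.1 into Section 7.1 and the pointer to Section 8.2 into Section 7.1.3.

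The cost is one deletion and two corrected references. Section 12.1 requires a written, approved amendment for any protocol change, so it is sensible to include this in the next one. No SAP change is needed.

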1.2.1.2 Clinical experience

The cumulative world-wide exposure with commercial deferasirox is estimated to be 383,491 Patient Years (PTY) as of October 31, 2017, and approximately 8,110 patients have been treated with deferasirox in Novartis-sponsored investigational clinical trials cumulatively since the Development International Birth Date (IBD).

Clinical studies have shown deferasirox to effectively chelate iron in patients with transfusional iron overload as demonstrated by decreases in liver iron concentration (LIC), serum ferritin, and cardiac iron (as assessed by magnetic resonance imaging [MRI] T2*) in patients with various underlying anemias (Nick 2003, Cappellini 2006, Vichinsky 2007, Porter 2008, Pennell 2010). Furthermore, deferasirox has been shown in various studies (ICL670A108, 2409, US02, US03, etc....) to be efficacious in reducing the iron overload in lower-risk MDS patients as measured by SF and/or LIC.

Deferasirox has demonstrated acceptable safety and tolerability in adult and pediatric patients with transfusional iron overload (Piga 2006, Cappellini 2006, Cappellini 2011). The most frequent reactions reported during chronic treatment with deferasirox in adult and pediatric patients included gastrointestinal disturbances in about 26% of patients (mainly nausea, vomiting, diarrhea, or abdominal pain) and skin rash in approximately 7% of patients. These reactions were dose-dependent, mostly mild to moderate, generally transient, and mostly resolve even if treatment is continued. Deferasirox can cause gastrointestinal hemorrhages, which can be fatal, especially in elderly patients who have advanced hematologic malignancies and/or low platelet counts.

Mild, nonprogressive increases in serum creatinine, mostly within the normal range, occurred in approximately 36% of patients. These were dose-dependent, often resolved spontaneously and some were alleviated by reducing the dose. Acute renal failure and increases in serum creatinine (≥ 2 x upper limit of normal ULN), have been reported following prescription use of deferasirox; these were usually reversible after treatment interruption. Renal tubulopathy has been reported with deferasirox. The majority of patients were children and adolescents with beta-thalassemia and serum ferritin levels $<1,500$ microgram/L.

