5.3 Exclusion criteria

Patients eligible for this study must not meet **any** of the following criteria:

1. Patients that receive more than one iron chelator at the same time as current iron chelation treatment. (Patients who have received combination therapy in their medical history but are currently being treated with a single ICT agent are eligible.)
2. Patients continuing on deferoxamine or deferiprone in addition to study treatment. (Patients switching to or continuing on deferasirox are eligible).
3. Unresolved adverse events if the patient was previously treated with deferiprone or deferoxamine or deferasirox.

4. Significant proteinuria as indicated by a urinary protein/creatinine ratio $> 0.5 \text{ mg/mg}$ in a non-first void sample urine measured at screening visit 1.
5. Serum creatinine $>$ age adjusted ULN measured at any screening visit
6. Creatinine clearance below 90 mL/minute measured at any screening visit. Creatinine clearance using the Schwartz formula will be estimated from serum creatinine measured at each respective visit.
7. ALT and/or AST $> 2.5 \times \text{ULN}$ measured at screening visit 1.
8. Total bilirubin (TBIL) $> 1.5 \times \text{ULN}$ measured at screening visit 1.
9. Patients with significant impaired GI function or GI disease that may significantly alter the absorption of oral deferasirox FCT (e.g. ulcerative diseases, uncontrolled nausea, vomiting, diarrhea, malabsorption syndrome, or small bowel resection).
10. History of and/or laboratory evidence of active Hepatitis B or Hepatitis C (HBsAg in the absence of HBsAb OR HCV Ab positive with HCV RNA positive).
11. Liver disease with severity of Child-Pugh Class B or C.
12. History of hypersensitivity to any of the study drug or excipients.
13. Patients participating in another clinical trial or receiving an investigational drug.
14. Patients with a known history of HIV seropositivity.
15. Patients unwilling or unable to comply with the protocol.
16. History of malignancy of any organ system, treated or untreated, within the past 5 years whether or not there is evidence of local recurrence or metastases, with the exception of localized basal cell carcinoma of the skin.
17. Significant medical condition interfering with the ability to partake in this study (e.g. uncontrolled hypertension, unstable cardiac disease not controlled by standard medical therapy, systemic disease: cardiovascular, renal, hepatic, etc.).

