These dosing tables have been constructed for each dosing group considering lower (5th) and upper (98th) percentiles from weight charts for children aged ≥ 2 to < 6 years. This is taking into account that the study will enroll male or female children, ≥ 2 and < 6 years. For patients with a low body weight and lower daily DFX dosing requirements (e.g. below 19 kg body weight in the 3.5 mg/kg/day dosing group) the needs will not allow for the use of the smallest tablet strength available. In such cases a written request will be sent to Novartis, to advise on the individual patient enrolment / dose adjustments options.

The patient will be dispensed deferasirox FCT in accordance with the protocol. For patients already well-managed on prior treatment with deferoxamine or deferasirox DT, a starting dose of crushed deferasirox FCT is outlined below in [Table 6-2](#).

Table 6-2 Equivalent dose of deferasirox FCT

ICT Dose Prior to Enrollment	Starting Dose		
	Deferoxamine (mg/kg/day)	Deferasirox DT (mg/kg/day)	Deferasirox FCT (mg/kg/day)
10	5	3.5	
20	10	7	
30	15	10.5	
40	20	14	
50	25	17.5	

Dose equivalence between deferiprone and deferasirox has not been established in clinical studies. For patients pre-treated with deferiprone, the starting dose of deferasirox FCT should be 14mg/kg/day.

Safety assessment will be performed weekly after treatment initiation and thereafter monthly during the study. Monthly serum ferritin values and trends will be used to adapt the treatment of the patients together with safety data.

Patients will continue therapy for 24 weeks.

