7.1.3 Run-in period

Any current iron chelation therapy except deferasirox will be discontinued to undergo a 5-day washout period prior to commencing the 24-week treatment period with crushed deferasirox FCT.

A second screening visit will occur for chelation naïve and patients treated with iron chelation therapy other than deferasirox as detailed in [Table 7-1](#).

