2.1.2.6 Baseline

For the **safety** and the **efficacy evaluations**, the last available assessment on or before the date of start of study treatment will be defined as baseline. If patients have no value as defined above, the baseline result will be missing.

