2.11 Safety analyses

As stated in the protocol (Section 10.5), the following secondary safety endpoints will be evaluated:

AEs suspected to be related to the crushed deferasirox FCT:

- Number and percentage of patients who experienced AEs suspected to be related to the study treatment up to 24 weeks including 30 day safety follow-up overall and by SOC, PT and severity (see [section 2.11.1](#)).

Overall safety of crushed deferasirox FCT:

- Number and percentage of patients with any AEs, SAEs, and AEs leading to discontinuation together with their severity up to 24 weeks including 30 days safety follow-up will be provided. Details regarding the analysis of AEs are described in [section 2.11.1](#).
- Absolute change from baseline over time will be provided graphically by box plots for serum creatinine, creatinine clearance, UPCR, total bilirubin, ALP, ALT, AST for each visit. Furthermore, shift tables using low/normal/high classification will be provided. Details regarding laboratory abnormalities are described in [Section 2.11.4](#). See [section 2.10.2](#) for the mapping of an unscheduled visit to a scheduled visit and box plots and shift tables will be generated for each scheduled visit only after mapping an unscheduled visit.

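### Laboratory change from baseline pools children whose baseline was taken on deferasirox with children newly starting it, so the pooled figure mixes two different changes

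*Protocol*

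**What the plan says.** Children already taking deferasirox may enter. Protocol 5.3 states: "Patients switching to or continuing on deferasirox are eligible". They do not stop the drug first. Section 4.1 says "Any current chelation therapy except deferasirox will be discontinued to undergo a 5-day washout period prior to commencing a 24 weeks treatment period", and section 7.1.3 repeats the exemption: "Any current iron chelation therapy except deferasirox will be discontinued to undergo a 5-day washout period". For those on dispersible tablets the starting dose is converted from the previous dose. Section 6.1 reads "For patients already well-managed on prior treatment with deferoxamine or deferasirox DT, a starting dose of crushed deferasirox FCT is outlined below in" Table 6-2.

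SAP 2.1.2.6 sets one baseline rule for every child: "the last available assessment on or before the date of start of study treatment will be defined as baseline".

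SAP 2.11 then plans, for all children together: "Absolute change from baseline over time will be provided graphically by box plots for serum creatinine, creatinine clearance, UPCR, total bilirubin, ALP, ALT, AST". It adds shift tables. SAP 2.11.4 adds descriptive summaries of change and counts of notable values. Two of the notable criteria in SAP Table 2-1 refer to baseline: creatinine (more than 33% above baseline and above ULN, at two consecutive measurements) and ALT/AST (more than 5 x ULN and more than twice baseline). SAP 2.3 and 2.11.2 mark subgroups as not applicable. These laboratory changes form part of a named secondary safety endpoint (Protocol Table 3-1, SAP Table 1-1).

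**The concern.** The word baseline covers two different states. For a naïve or washed-out child it is a value before this course of deferasirox, so the later change includes the effect of starting the drug. For a child who goes straight from existing deferasirox treatment to crushed FCT it is an on-drug value, so the later change is what happens on changing formulation while treatment continues. Protocol 7.2.2.5.2 says "Renal parameters are monitored weekly to establish a reliable pretreatment baseline", but continuing children have no drug-free value.

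No quota fixes how many of the minimum 40 children belong to each group, so the weight of each component depends on who happens to enrol. A pooled mean change near zero could be read as showing that starting crushed FCT has little renal effect, when it may partly reflect on-drug baselines.

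Elsewhere the plan does treat the groups as distinct. Protocol 5.2 gives them different ferritin thresholds, Table 7-1 reserves the second screening visit for children newly starting deferasirox, and SAP 2.13 presents observer-reported change scores separately for children pre-treated with deferasirox. The laboratory outputs have no such separation.

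**Working it through.** **Nearest stated figure.** The plan gives no expected laboratory change, so there is none to reproduce. Its only related calculation is Table 10-1, the chance of at least one case among 40 children: 1 − (1 − p)^40. At p = 3% this gives 1 − 0.97^40 = 0.704, against a stated 0.70, so the table's formula is confirmed. It is reused below.

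**Pooled mean change.** Let f be the share of children on deferasirox at entry, D the mean change in new starters, and r the change in continuing children as a fraction of D. The documents give none of the three. They are assumptions, shown as a range.

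Pooled mean = (1 − f) × D + f × r × D, so pooled mean / D = (1 − f) + f × r.

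| f | New starters of 40 | r = 0 | r = 0.5 | r = 1 |
|---|---|---|---|---|
| 0.25 | 30 | 75% | 87.5% | 100% |
| 0.50 | 20 | 50% | 75% | 100% |
| 0.75 | 10 | 25% | 62.5% | 100% |

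At f = 0.5, for example: 0.5 + 0.5 × 0 = 0.50, and 0.5 + 0.5 × 0.5 = 0.75. There is understatement only if r is below 1. With r above 1 the pooled mean would overstate D.

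**Is r below 1 plausible?** For renal parameters, yes. Protocol 1.2.1.2 calls the creatinine increases dose-dependent, and children coming from dispersible tablets start on a converted dose. They have also passed the creatinine, creatinine clearance and urine protein/creatinine ratio (UPCR) exclusions of section 5.3 while on drug. For the liver the argument is weaker, because section 1.2.1.2 describes transaminase elevations as not dose dependent and says most affected patients had raised levels before deferasirox.

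**Notable creatinine counts.** The closest figure to the SAP criterion is in Protocol 1.2.1.2: 3.1% of children aged 2 to under 6 years rose by more than 33% and above ULN on at least two consecutive occasions. That study ran for 5 years, with a mean exposure of 44.1 months (section 1.2), so the rate over 24 weeks may be lower. Taking 3.1%:

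- All 40 children: 40 × 0.031 = 1.24 expected cases; chance of any = 1 − 0.969^40 = 0.72.
- 20 new starters (f = 0.5): 20 × 0.031 = 0.62 expected; chance of any = 1 − 0.969^20 = 0.47.

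A split of the notable counts will therefore show very few cases. The main gain is in the mean changes, box plots and shift tables.

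**The case against.** The strongest reply is that the pooled figure is not wrong. The objective is the overall safety of crushed FCT, and the regulator's question was about young children when tablets are crushed (Protocol 2.1). For a child switching formulation, the last value before crushed FCT is the natural reference. No document sets out to estimate the laboratory effect of starting deferasirox. This stands: the pooled value is the average change after moving to crushed FCT in the mix that enrols. It does not remove the need to keep that change apart from the change in new starters when the results are interpreted.

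It is also fair that r = 0 has no source. Doses can be adjusted during the study up to 28 mg/kg/day (section 6.3.1.4), so continuing children may change too.

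Two stronger readings are tempting. A reader might take the statement "Mild, nonprogressive increases in serum creatinine, mostly within the normal range, occurred in approximately 36% of patients" as the rate in new starters and calculate how far pooling lowers it. The documents do not support that: the figure covers adult and pediatric patients, is not limited to new starters, and concerns rises mostly within the normal range, which is not the SAP criterion. A reader might also assume that creatinine is already raised at an on-drug baseline and multiply that rise into the 33% threshold. No document gives such a rise, and the criterion also requires a value above ULN, which does not depend on baseline.

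Listings of laboratory data and of prior chelation would allow patient-level separation, but no planned summary crosses the two. The adverse-event split dropped in SAP section 4 would not have helped: it compared naïve with non-naïve children, placing washed-out children with continuing ones, and did not cover laboratory data.

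**Conclusion.** The point holds as a matter of presentation and interpretation. The missing washout, the common baseline rule and the pooling are all documented. That pooling understates the new-starter change is an inference. It requires continuing children to change less than new starters, which is plausible chiefly for creatinine, creatinine clearance and UPCR. Its size cannot be derived from the documents; at an even mix the illustration runs from 50% to 75% of the new-starter change, and there is no understatement if both groups change equally.

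The scope is limited. Criteria that do not use baseline (creatinine clearance below 60 mL/min, UPCR above 1.0, bilirubin above 2 x ULN, potential Hy's law) and the primary gastrointestinal endpoint are not affected. The point applies to children on deferasirox at entry, not to those who had stopped it well before. A reader might infer that the laboratory safety analysis as a whole is invalid, or that liver signals are hidden to the same degree as renal ones. The documents support neither.

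**What to change.** In SAP 2.11 and 2.11.4, present the planned change-from-baseline summaries, box plots and shift tables (chiefly creatinine, creatinine clearance and UPCR), and the notable counts that use baseline, in two groups plus total:

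1. On deferasirox at entry, labelled as change during continued deferasirox after moving to crushed FCT.
2. Newly starting deferasirox (naïve or washed out).

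Base any statement about starting the drug on the second group. State how time since last deferasirox dose assigns a child to a group.

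The cost is SAP wording and one by-group variable. Prior chelation is already collected, and SAP 2.7.1.1 already plans to summarise time from last chelation to study start. No new data and no change to clinical management are needed. The downside is small descriptive groups, with about one notable creatinine case expected in 40 children at 3.1%, so the split counts should be read as description only.
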